The purpose is to investigate the relationship between high total intake of systemic steroids in patients with upper and lower airway disease, low endogenous cortisol production, and reduced bone density and structure. Additionally, through an exploratory follow-up (pilot project) study, to investigate whether improved adherence to local steroid treatment and biologic medication would decrease the patient's endogenous cortisol production.

Hypothesis/research question:

Patients with CRS/CRSnNP/CRSwNP who have received systemic steroids have an impact on the adrenals with low basal P-cortisol (below 500nmol), abnormal response to stimulation with ACTH (synacthen test) measured at the final P-cortisol. Additionally, a reduced increase (delta value) in P-cortisol is expected in connection with a synacthen test. These patients also have an affected bone density and structure with a higher incidence of osteopenia and osteoporosis than expected for this age group. Patients with CRS/CRSnNP/CRSwNP who can improve their adherence to >80% have an increasing impact on P-cortisol.

Primary outcome:

The primary outcome is to investigate whether newly referred patients with upper and possible lower respiratory tract diseases have an impact on their own cortisol production after prolonged use of systemic steroids. That is, the baseline level of plasma cortisol is <500 nmol, and a correlation with lifelong use of systemic steroids can be demonstrated.

Secondary outcomes:***Cross-sectional study:***

- 1: After a stimulation test, plasma cortisol is not above 500 nmol.
- 2: The increase in plasma cortisol is associated with the intake of systemic steroids.
- 3: Demonstration of the correlation between lifelong use of systemic steroids and the degree of osteopenia and osteoporosis (T-score). T-score from DEXA scanning is used to measure bone density and structure. An affected T-score is defined as follows: T-score between -1.0 and -2.5 = osteopenia and score \leq -2.5 = osteoporosis.
- 4: The number of patients with osteoporosis/penia of the spine and femur is increased compared to expected findings in age-matched individuals.

Exploratory follow-up at 4 months (pilot project):

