- 5: Patients with CRSwNP/CRSsNP/CRS with and without asthma who have shown low adherence <80% after the cross-sectional study and who have achieved adherence over 80% at follow-up have also developed adrenal function impairment with a reduction in plasma cortisol of at least 8% (exploratory study).

Study design (brief description):

The study design is a cross-sectional study of newly referred patients to the Luftvejsklinik, ENT, RH for investigation and treatment of CRS and possibly asthma. And an exploratory follow-up (pilot project) study of patients who attend 4-month control.

Background:

Chronic rhinosinusitis (CRS) is a condition with chronic inflammation in the nose and sinuses. CRS can be with both nasal polyps (CRSwNP) and without polyps (CRSsNP) (5). 9% of the Danish population is affected by CRS, and about 4% are estimated to be diagnosed with CRSwNP (1). The diagnosis is based on the patient's symptoms and objective signs of inflammation in the nose and sinuses. The symptoms are a blocked nose or nasal secretion, reduced airflow, reduced sense of smell, pain/pressure around the nose, forehead, or eyes. The above symptoms must have been present for more than 12 weeks, and one of the symptoms must be secretion or reduced airflow through the nose to make a diagnosis (6). About 40% of CRS patients in primary care have asthma, whereas 65% referred for treatment at the hospital have asthma (7). CRSwNP that is not satisfactorily controlled particularly affects quality of life (8). It is often characterized by type-2 inflammation, i.e., an increased number of eosinophils in the mucous membranes in the sinuses and nasal polyps - as well as comorbidities such as asthma, ASA/NSAID intolerance (N-ERD), and allergies (5). CRS can be treated both surgically and medically. The basic medical treatment of CRS includes daily saline irrigation and use of nasal steroids. If there is a lot of secretion, antibiotic treatment can also be added to the basic treatment. In the case of nasal polyps, systemic corticosteroid treatment (prednisolone tablets/injection betamethasone) can also be added (5,6). If the medical treatment is not

optimal, patients can be offered surgical treatment - endoscopic sinus surgery (ESS) (5). The goal is to aim for the removal of polyps in the nose and sinuses.

Comorbidity:

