The Synacthen test is performed by inserting a venous catheter at time 0, and then a blood sample is taken to determine the plasma cortisol level. Subsequently, 0.25 mg of ACTH is injected into the venous catheter, and 5 ml of iso NaCl is flushed. After 30 minutes, a blood sample is taken to determine the plasma cortisol level. The first mL should be discarded before obtaining a new P- Cortisol is taken. The 0-sample and 30-sample belong to the same Sampling Test Form (PTB). Scanned with PDA corresponding to the actual sampling time. The blood samples are sent together with their corresponding PTBs for analysis at the Clinical Biochemical Department, RH. Results will appear in the patient's medical record under laboratory results. The patient must not have ingested hydrocortisone or steroid inhalation at least 12 hours before the test and should not have received treatment with injection (i.m) steroid such as diprospan within the last three months (30). The entire procedure for the synacthen test takes approximately 1 hour and 15 minutes, including preparation and completion. The test itself takes about 30 minutes. This applies to both the cross-sectional study and exploratory follow-up.

DEXA scan:

Patients with CRS/CRSsNP/CRSwNP receive a DEXA scan as part of their clinical evaluation. This group has received larger amounts of nasal steroid for often more than 10 years, as well as 1-3 times systemic steroid annually over several years. Therefore, it is good clinical practice to refer to a DEXA scan to examine bone density and structure and any need for treatment with calcium and vitamin D. These investigations are included in the project.

Questionnaires:

Patients are required to complete the following questionnaires as part of the standard treatment in the Respiratory Clinic:

- STARR-15
- SNOT-22:
- ACQ
- ACT
- MARS 5-L/N:
- Foster score

Data processing:

Data will be entered into REDCap (Research Electronic Data Capture), which is a secure web application for building and managing databases and online questionnaires. The system was developed at Vanderbilt University, which released the first version in 2008 (31). The use of REDCap is a requirement from Region Hovedstaden.

Statistical analysis:

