Statistical analysis of the data will be performed using IBM SPSS Statistics. Results will be presented as mean, SD, median, range, and 95% CI. Parametric data will be compared using paired tests, and non-parametric data using Mann-Whitney Test. Categorical variables will be tested using the chi-square test.

Power calculation for cross-sectional study and exploratory follow-up at 4 months (pilot project):

Rationale: In a recent study on severe asthma, patients received daily tablet prednisolone (>5 mg) for 3 months. 60% of the patients had adrenal insufficiency, 33% had total insufficiency, and 27% had partial insufficiency (32). Patients with CRS are often treated with steroid injections in Denmark, receiving an average of three steroid injections per year (clinical observation, REDCap, Global airways incl. biological treatment). Some receive up to six injections per year, with an effect lasting approximately 6-8 weeks per injection. This means that patients with CRS are only covered for about 6 months out of 12 months per year. This is different from severe asthma with daily treatment. Therefore, we estimate that we can detect half of the findings from the asthma study (32). We therefore expect that half of the 60% who develop insufficiency in the asthma study = 30% of the CRS patients will have adrenal insufficiency. As some will have received steroid injections several months ago, a slight reduction is estimated to 25%. But no less than 25%, as many receive high-dose nasal steroids, which, like steroid cream, may cause adrenal insufficiency (3). The 25% is our best estimate. It may be higher but not lower. The literature has documented that 8% of a population have adrenal insufficiency without having received supplemental steroids before the test. To

demonstrate a difference between the background population and our population with 25% adrenal insufficiency, we will need to investigate 72 patients with an alpha value of $p < 0.05$ and a power of 80%, and with a dropout rate of 10%, we will need to test around 80 patients (cross-sectional study).

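### The stated 80% power is for an undefined adrenal insufficiency rate in a two-group layout; it is not shown to apply to either half of the primary outcome in the one enrolled group

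*Protocol*

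**What the plan says.** Under Primary outcome, the Protocol sets two requirements on the unstimulated sample: "That is, the baseline level of plasma cortisol is <500 nmol, and a correlation with lifelong use of systemic steroids can be demonstrated". Under Secondary outcomes, item 1 applies the same 500 nmol value to the stimulated sample: "After a stimulation test, plasma cortisol is not above 500 nmol". The Synacthen test section has every patient sampled at 0 and at 30 minutes, so both values will exist.

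The power calculation section works with a different term. It starts from an asthma study with 60% insufficiency and reasons that "half of the 60% who develop insufficiency in the asthma study = 30% of the CRS patients will have adrenal insufficiency". It then lowers this to 25%. For the reference it says: "The literature has documented that 8% of a population have adrenal insufficiency without having received supplemental steroids before the test". The target is to "demonstrate a difference between the background population and our population with 25% adrenal insufficiency, we will need to investigate 72 patients", at alpha 0.05 and 80% power, rising to about 80 patients for 10% dropout.

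On layout, the Study design section says: "The study design is a cross-sectional study of newly referred patients to the Luftvejsklinik, ENT, RH". No recruited comparison group is described.

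**The concern.** A sample size justification should concern the variable that the primary outcome tests. Here the two sections do not meet. The primary outcome is a proportion on the time-0 sample plus a correlation. The power calculation is for a condition that it ties to no sample and no threshold. The background section on adrenal insufficiency describes it by mechanism only, so it does not supply the link.

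The gap matters because the Protocol uses 500 nmol on two samples. If cortisol does not fall after ACTH, every patient at or below 500 nmol at 30 minutes was also at or below it at time 0. The time-0 rate is then at least the stimulated rate, values of exactly 500 aside. One figure of 25% fits both only if almost nobody crosses 500 nmol on stimulation. The Protocol does not say which of the two the 25% describes.

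At stake is how the result is read. A finding on baseline cortisol, or on the correlation, could be presented as resting on 80% power that was never calculated for it. With both samples in hand, the meaning of insufficiency could also be settled after the data are seen.

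**Working it through.** **Inputs.** From the power calculation section: p1 = 0.25, p0 = 0.08, alpha 0.05, power 0.80, dropout 10%. The Protocol does not state sidedness; two-sided is assumed, so z = 1.960 and 0.842, with sum 2.802.

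**1. Reproducing 72 (two equal groups).**
- Unpooled variance: n = (0.25×0.75 + 0.08×0.92) × 2.802² / 0.17² = 0.2611 × 7.849 / 0.0289 = 70.9, so 71 per group.
- Pooled null variance, mean rate 0.165: n = [1.960×√(2×0.165×0.835) + 0.842×√0.2611]² / 0.0289 = 73.6, so 74 per group.
- The arcsine method gives 70 per group. Power at 72 per group is 79.1%.
- Dropout: 72 / 0.9 = 80, as stated.

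The stated 72 is therefore a per-group number for a two-group comparison.

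**2. The same contrast for one group against a fixed 8%.**
- Null and alternative variance: n = [1.960×√(0.08×0.92) + 0.842×√(0.25×0.75)]² / 0.0289 = 27.8, so 28.
- Arcsine: 35. Alternative variance only: 0.1875 × 7.849 / 0.0289 = 50.9, so 51.
- Exact binomial at n = 72: reject at 12 or more events (upper-tail probability 0.011 under 8%); power under 25% is 0.966.

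None of these one-group methods gives 72.

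**3. First half of the primary (time-0 cortisol below 500 nmol).** The Protocol gives neither an expected nor a reference rate, so no power follows from it. As pure illustration, with assumed reference and trial rates and a one-sample normal approximation at n = 72, power is 84% for 50% vs 67%, 59% for 80% vs 90%, and 23% for 90% vs 95%. These show only that power does not carry over from one pair of rates to another.

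**4. Second half (correlation).** No target coefficient or method is given. Under a Pearson analysis with Fisher's z, the smallest |r| with 80% power is tanh(2.802/√(n−3)):
- n = 72: tanh(2.802/√69) = 0.325
- n = 80: tanh(2.802/√77) = 0.309

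At n = 72, power is 73% for an assumed r of 0.30 and 39% for 0.20. These are sensitivity values.

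**The case against.** The strongest reply is that this is planning text. The Primary outcome section already fixes the sample and cut-off for the primary proportion, and a vague planning rate biases no estimate, test or interval. Both sections concern the same clinical idea, impaired cortisol production. Sizing a study on one component and leaving an association unsized is common in cross-sectional work. All of that is fair. It limits the consequence but does not supply the missing link: if insufficiency is meant to be the Synacthen result, the 80% belongs to secondary outcome 1; if it is meant to be the baseline value, the Protocol does not say so.

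Three stronger readings are tempting and are not supported.
- A reader might infer that the trial is underpowered. For 25% against a fixed 8% it is not. For the two halves of the primary the documents give no rates and no target coefficient from which to judge.
- A reader might infer that it is unclear whether total or partial insufficiency counts, and that counting only the total grade would leave power low. The power calculation settles this: it halves the full 60%, which is 33% total plus 27% partial, so both grades count. It also says that the 25% may be higher but not lower. Narrowing the trial rate while leaving the 8% as it is would compare unlike quantities.
- A reader might object to having separate outcomes on the baseline and stimulated samples. That is legitimate in itself.

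**Conclusion.** The point holds in this form: the stated power and size are attached to a quantity not shown to be the primary outcome, and to a two-group layout that the design does not describe. The arithmetic behind 72 and 80 is sound for two groups. For the one enrolled group against a fixed 8%, true power at 72 is about 97%, higher than stated. For baseline cortisol below 500 nmol, power cannot be computed from the Protocol, and the size of any gap is unknown. For the correlation, 80% power at 72 requires |r| of about 0.325.

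These results assume two-sided alpha 0.05 and, for the correlation only, a Pearson/Fisher-z analysis; the Protocol names no correlation method and foresees non-parametric data. The text should be corrected before analysis. The point casts no doubt on the data to be collected.

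**What to change.** Amend the Primary outcome and power calculation text before analysis:

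1. State which cortisol sample and cut-off the 25% and 8% refer to. Reconcile the two sections so that the sized proportion and the primary proportion are the same variable. Otherwise, give expected and reference rates for time-0 cortisol below 500 nmol and restate the power on those rates.
2. Restate the power for one group against a fixed reference rate (about 97% at 72 for 25% vs 8%), or say that a comparison group is meant and describe it.
3. State that the 80% power does not cover the correlation half. Optionally add, as sensitivity, that 72 patients give 80% power only for |r| of about 0.325 or more under a Pearson/Fisher-z analysis.

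Which cortisol definition is clinically right is for the investigators and is not proposed here. The cost is a text amendment and possibly a less favourable power statement for the primary outcome. If the one-group design stands, no new patients, visits or samples are needed, because both cortisol values and the total systemic steroid amount are already collected.

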Protocol - Adherence in Global Airways – the relationship between steroid intake and the impact on the endocrine axis, bone density, and structure in patients with chronic sinusitis and asthma

Research Group:

Clinical Nurse Specialist, Cand. Cur, [name] (PI)

Clinical Nurse Specialist, Cand. Cur, [name]

Chief physician and Ph.D., Ear-Nose-Throat, [name]

Professor and Chief physician, Endocrinology, [name]

Professor and Chief physician, Pulmonology, [name]

Introduction:

There has been a significant focus on ensuring treatment of diseases in both upper and lower airways (global airways) simultaneously because they have the same inflammatory disease mechanism.

Approximately 9% have chronic sinusitis (CRS), 4% of the Danish population is diagnosed with CRS with nasal polyps (CRSwNP)(1), and 7-10% have asthma. Over the years, some of these patients have been treated with systemic and/or locally acting steroids (glucocorticoids). These patients referred have moderate to severe disease with a significant disease burden, and therefore continue to be treated with steroids. The risk of developing secondary adrenal insufficiency is high with prolonged use of systemic high-dose and potent glucocorticoids but can also occur with locally administered glucocorticoids (2). It has recently been demonstrated that treatment of eczema with steroid-containing creams has indications of side effects not only on the skin but also on the bones (3). Moreover, there is an additive effect, so that it is the total burden of steroid intake that is significant for the development of side effects, but whether it also affects cortisol response to ACTH is unknown (4). Treatment with steroids currently affects the endocrine axis (P-cortisol), increasing the risk of osteopenia, osteoporosis, and possibly diabetes. Our knowledge of which preparations, doses, and modes of administration cause these side effects is inadequate, and whether the total dose over time is significant is unknown. This gives rise to conducting a cross-sectional study to determine the significance of these side effects, followed by an exploratory follow-up study of patients with global airway diseases and high adherence (80%) to local treatment.

Purpose:

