
Method:

Regarding 1) In the cross-sectional study, patients will receive the standard investigation and treatment at the Luftvejsklinik. This includes investigation for airway disease and possible type-2 inflammation,

treatment, etc. Measurement of their adherence and possible optimization of CRS and asthma treatment. The total amount of systemic steroids will be calculated and included in the study.

Experimental intervention (synacthen test): To investigate how prolonged use of systemic steroids and adherence affect cortisol production, all patients who agree to participate in the project will undergo a synacthen test. A synacthen test is used to assess whether the body's adrenal glands produce cortisol satisfactorily (i.e., own production). Cortisol is a hormone produced in the adrenal glands and is therefore called adrenal cortex hormone. It has a few effects, including on muscles, supportive tissues and bones, and nutrient metabolism. Therefore, the adrenal glands' ability to produce hormones is important. Reduced or absent production of adrenal cortex hormones can be seen with prolonged treatment with systemic steroids (adrenal cortex hormones). A synacthen test will be performed twice in total on all patients. The first time is at the 1st visit (preliminary examination) and the second time at the 4-month follow-up.

Ad 2) Exploratory investigation/4-month follow-up (pilot project): The experimental intervention in the follow-up involves measuring P-cortisol in patients who have now achieved high adherence (> 80%). Patients will receive standard follow-up/monitoring and treatment in the respiratory clinic.

Study population:

The study population consists of patients referred to the Luftvejsklinik, ENT, RH, for evaluation of CRS/CRSwNP/CRSnNP and with or without asthma for biological treatment. They are classified according to the type of inflammation they have (type-2 or non-type-2), whether they have CRSwNP or CRSsNP, their adherence, comorbidity with asthma, and finally the severity of the disease. All patients are given standard questionnaires to assess CRS/CRSwNP/CRSnNP and asthma (STARR-15, SNOT22, ACQ, ACT, MARS-5-L/N, Fosterscore - routine questionnaires for all patients in the Luftvejsklinik).

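### Secondary outcome 3 correlates lifetime steroid use with T-score without naming age adjustment, so age alone could produce the correlation

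*Protocol*

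**What the plan says.** Under Secondary outcomes, cross-sectional study, item 3 reads "Demonstration of the correlation between lifelong use of systemic steroids and the degree of osteopenia and osteoporosis (T-score", with the T-score taken from DEXA. No covariate, stratification or age-referenced bone score is attached to it. The Statistical analysis section says "Parametric data will be compared using paired tests, and non-parametric data using Mann-Whitney Test", adds the chi-square test for categorical variables, and names no method for a correlation.

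The exposure is a cumulative one. The Method section says "The total amount of systemic steroids will be calculated and included in the study", and the DEXA scan section describes the patients' history "as well as 1-3 times systemic steroid annually over several years". The rationale for the power calculation adds "Some receive up to six injections per year".

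Elsewhere the protocol does relate bone to age. The Hypothesis section expects "a higher incidence of osteopenia and osteoporosis than expected for this age group", and item 4 asks whether the number of affected patients is "increased compared to expected findings in age-matched individuals". Age and gender are on the list of demographic data. Eligibility for the cross-sectional study sets a lower age limit of 18 and no upper limit.

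**The concern.** A lifetime total can only grow with time, so older patients have had longer to build one up. If T-score is also lower in older patients, dose and T-score will be negatively correlated even where steroids have no effect on bone. Analysed as worded, outcome 3 cannot tell these two explanations apart.

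This matters because outcome 3 is the only bone outcome that uses dose. The Introduction names as an open question "whether the total dose over time is significant is unknown", and outcome 3 is where the study would answer it for bone. Outcome 4 takes age into account but does not use dose, so it cannot stand in for outcome 3. At stake is the reading of one secondary outcome: an age gradient reported as a steroid dose–response in bone.

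**Working it through.** **Inputs from the protocol.** The only sample size is 72 evaluable patients, or 72 / (1 − 0.10) = 80 with 10% dropout. It was set for adrenal insufficiency (25% against 8%), and no figure is given for outcome 3. Alpha is 0.05, taken here as two-sided.

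**Assumed inputs.** The protocol gives neither the age–dose nor the age–T-score correlation. The ranges used are 0.1 to 0.5 for age–dose and 0.2 to 0.5, in absolute value, for age–T-score. The negative sign of the second is also an assumption: the protocol treats bone status as age-dependent but does not state the direction.

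**Step 1: correlation produced by age alone.** With no steroid effect,

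r(dose, T) = r(age, dose) × r(age, T).

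For 0.3 and −0.3 this is −0.09; for 0.5 and −0.5 it is −0.25.

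**Step 2: false-positive rate of the crude test.** With Fisher's z and standard error 1/√(n − 3), let δ = atanh(|r|) × √(n − 3). The rate is Φ(δ − 1.96) + Φ(−δ − 1.96).

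Example at n = 72, |r| = 0.09: δ = 0.0902 × √69 = 0.750, and the rate is Φ(−1.210) + Φ(−2.710) = 0.113 + 0.003 = 11.6%.

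All cells at n = 72:

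| age–dose | age–T 0.2 | 0.3 | 0.4 | 0.5 |
|---|---|---|---|---|
| 0.1 | 5.3% | 5.7% | 6.3% | 7.0% |
| 0.2 | 6.3% | 7.9% | 10.2% | 13.3% |
| 0.3 | 7.9% | 11.6% | 17.0% | 24.1% |
| 0.4 | 10.2% | 17.0% | 26.8% | 39.1% |
| 0.5 | 13.3% | 24.1% | 39.1% | 56.4% |

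At n = 80 the rows run 5.4–7.2%, 6.4–14.2%, 8.2–26.4%, 10.8–42.8% and 14.2–61.1%. A larger sample makes the problem slightly worse, because the induced correlation is a bias and not noise.

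**Step 3: simulation.** Normal variables with linear age effects were simulated, 40,000 samples for each of the 20 pairs at n = 72. The crude Pearson test rejected in 5.4% to 57.4% of samples, which agrees with the formula. The correlation with age partialled out rejected in 4.8% to 5.2% in every cell. When age and dose are unrelated, the crude test also stays at 5%.

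**Step 4: is 0.1 to 0.5 plausible for age–dose?** Dose was modelled as courses per year × years of disease, with 1–3 courses a year (DEXA scan section) or 1–6 (upper figure in the power rationale). The age and duration distributions are assumptions.

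| Duration of disease | Age uniform 20–80: 1–3 / 1–6 | Age normal, mean 50, SD 13, cut at 18: 1–3 / 1–6 |
|---|---|---|
| Onset uniform from 18 to current age | 0.58 / 0.54 | 0.48 / 0.44 |
| Same, capped at 10 years | 0.42 / 0.36 | 0.26 / 0.22 |
| 1–20 years independent of age, limited to years since 18 | 0.20 / 0.18 | 0.09 / 0.08 |

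The span is 0.08 to 0.58, so 0.1 to 0.5 is a fair display range, with weak links possible when duration hardly depends on age.

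**The case against.** The strongest reply is that covariates for a secondary outcome are commonly left to a statistical analysis plan, and one may exist that was not available here. The Statistical analysis section names no correlation method, so its silence does not show that age will be ignored. The word correlation may also be meant loosely: an age-adjusted regression or partial correlation would arguably fit the present wording. This stands as a limit. The protocol does not forbid adjustment, and the point is not that a model is missing. But the outcome itself is stated as a correlation with no mention of age, and a crude coefficient would satisfy it. The crude and the age-adjusted association are different quantities, so the outcome definition is the place to say which is meant.

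The second reply is that the size is assumed throughout. Both correlations, and the sign of one, come from outside the protocol, and the rates presuppose a Pearson-type test on continuous T-score. That is correct. The table shows what could happen, not what will, and its lower end is almost nominal. The 56% figure needs both correlations at 0.5 and should not be quoted alone.

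Third, age is collected, so adjustment remains possible at analysis. That is true, and it is why the change is cheap. Adjustment chosen after the data are seen would carry less weight than adjustment stated now.

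**Conclusion.** The concern holds as a wording weakness in one secondary outcome. Nothing in the protocol handles age for outcome 3, although the hypothesis and outcome 4 show that age is considered relevant to bone. With no steroid effect and 72 patients, the crude test's false-positive rate would lie between 5.3% and 56.4% over the assumed ranges, and near 12% with both correlations at 0.3. It is close to 5% if age and dose are only weakly related. Adjusting for age restores about 5% throughout, given linear age effects as simulated. Outcome 4 is not affected in this way. Confidence is moderate, because the age correlations in this population are unknown and an unseen analysis plan might already adjust.

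**What to change.** Restate outcome 3 as the association of continuous T-score with cumulative systemic steroid dose, adjusted for age and sex, estimated by linear regression or partial correlation and reported with a 95% confidence interval. The calculations above cover age only; sex is added because it is also on the list of collected data. A model that also includes weight can serve as a sensitivity analysis, not the main one, because weight may itself be affected by steroids.

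The cost is the wording of one outcome and no new data. In degrees of freedom, the smallest correlation detectable with 80% power at n = 72 is tanh(2.8016 / √69) = 0.3250 unadjusted, tanh(2.8016 / √68) = 0.3272 with age, and tanh(2.8016 / √67) = 0.3295 with age and sex.

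If age and dose correlate at 0.1 to 0.5, the variance of the dose coefficient rises by 1 / (1 − r²), which is 1.01 to 1.33. The T-score variance explained by age offsets this in part or in full: with both correlations at 0.5 the net factor is 1.33 × 0.75 = 1.00, and with 0.5 for age–dose and 0.2 for age–T-score it is 1.33 × 0.96 = 1.28.

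### Outcome 5 equates an unexplained 8% fall in cortisol with adrenal impairment and names no sample, unit of analysis, comparator or link to the 500 nmol level

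*Protocol*

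**What the plan says.** Item 5 under Secondary outcomes (exploratory follow-up at 4 months) concerns patients with low adherence at first "who have achieved adherence over 80% at follow-up". It states that they "have also developed adrenal function impairment with a reduction in plasma cortisol of at least 8" per cent. The item does not mention 500 nmol, the sample to be used or a comparison group.

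Three nearby statements judge adrenal impact by an absolute level:

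- Hypothesis: patients given systemic steroids "have an impact on the adrenals with low basal P-cortisol (below 500nmol" nmol).
- Primary outcome: "the baseline level of plasma cortisol is <500 nmol".
- Secondary outcome 1: "After a stimulation test, plasma cortisol is not above 500 nmol".

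The Synacthen test section gives one sample at time 0 and one later: "After 30 minutes, a blood sample is taken to determine the plasma cortisol level". The clock time is recorded ("Scanned with PDA corresponding to the actual sampling time"), but no time-of-day window is set. The Method section schedules two tests: "The first time is at the 1st visit (preliminary examination) and the second time at the 4-month follow-up".

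The last paragraph of the power calculation section plans to compare P-cortisol change under good adherence with change under continued poor adherence. It says that the effect of good adherence on adrenal function is unknown.

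**The concern.** Item 5 attaches a diagnostic label to a relative change without tying that change to the level the Protocol uses for adrenal impact. Two analysts could follow it and report different results, because the sample and the unit of analysis are both open.

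If it is applied patient by patient, ordinary variation between two single samples four months apart could produce many falls of 8%. The wording covers improvers only, so item 5 by itself would not show how often the same fall occurs in patients whose adherence stayed poor. The pilot is meant to inform a possible later study on adherence, so an ambiguous impairment statement could be carried forward.

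**Working it through.** **1. Basis for 8%.** The Protocol gives no calculation for it. Its other 8% figures are prevalences of adrenal insufficiency: one in patients on inhaled steroids (background section), one in people not given supplemental steroids (power calculation). Neither is a change in cortisol. The stated sample size (72, about 80 with dropout) concerns 25% versus 8% prevalence in the cross-sectional study and does not bear on item 5.

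**2. The 8% rule beside the 500 nmol level.** The illustrative values below apply to either sample.

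| First → second (nmol) | Change | Fall of at least 8%? | Position against 500 |
|---|---|---|---|
| 800 → 736 | −8.0% | yes | above both times |
| 510 → 490 | −3.9% | no | crosses from above to below |
| 400 → 368 | −8.0% | yes | below both times |

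The boundary is 500 / 0.92 = 543.5, so any first value of about 544 or more can fall by exactly 8% and remain above 500.

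**3. Per-patient reading, no true change.** Assume log-normal within-person variation and one sample per visit. With σ = √ln(1 + CV²), the log ratio of two samples has SD √2·σ, so

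P(fall ≥ 8%) = Φ( ln 0.92 / (√2·σ) ), where ln 0.92 = −0.0834.

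For CV 10%: σ = 0.0998, √2·σ = 0.1411, −0.0834 / 0.1411 = −0.591, P = 0.277.

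**4. Group-mean reading, no true change.** For the mean log ratio of n improvers,

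P = Φ( √n · ln 0.92 / (√2·σ) ).

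For CV 10% and n = 40: −0.591 × 6.325 = −3.74, P ≈ 0.01%.

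| Assumed CV | Per patient | Group mean, n = 40 | Group mean, n = 20 |
|---|---|---|---|
| 5% | 12% | <0.01% | <0.01% |
| 10% | 28% | 0.01% | 0.4% |
| 15% | 35% | 0.6% | 4% |
| 20% | 38% | 3% | 9% |
| 30% | 42% | 10% | 18% |

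The CVs and the numbers of improvers are assumptions; the Protocol gives neither. On the per-patient reading, the CV would have to be about 3.6% or less to hold the chance rate at 5%.

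**5. Would a simple crossing of 500 do better?** Under the same model, a patient first measured at 520 falls below 500 with probability Φ( ln(500/520) / (√2·σ) ). This is 39% at CV 10% and 44% at CV 20%. Near its limit that count is just as exposed to noise.

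**The case against.** The strongest reply is that item 5 reads as a hypothesis about a group and not as a responder rule. It mentions no proportion or count, whereas item 4 explicitly refers to a number of patients. The power calculation section describes the follow-up as a comparison of P-cortisol change between adherence groups. On that reading the chance rates largely collapse (step 4). Random variation also affects the poor-adherence group, so the planned comparison would expose it. This stands, and it rules out several stronger inferences.

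- A reader might infer that the pilot will report impairment in a third or more of unchanged patients. The text does not fix a per-patient rule, the CV is assumed, and a comparator is planned elsewhere.
- A reader might infer that the Protocol uses 500 nmol everywhere else. It does not: the hypothesis also uses a reduced rise in cortisol, item 2 uses the increase, and the power calculation speaks of insufficiency with no cut-off. The 500 level is applied to the basal sample in one place and the stimulated sample in another, and both outcomes that use it belong to the cross-sectional part. The two measures are unreconciled, which is less than a flat contradiction.
- A reader might infer that 8% was carried over from the prevalence figures, or that the resulting figure is committed to a later design. The Protocol says neither; it mentions only a possible future study.

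Covariate adjustment is commonly left to an SAP, and its absence is not held against the Protocol. The outcome's own wording is different: the label, the threshold and the population are written here, while the sample and the comparator are left out. The group reading does not remove the lack of a basis for 8% or the gap between the label and the 500 nmol level.

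**Conclusion.** The point holds as a defect of definition. Item 5 calls a fall of at least 8% adrenal impairment, gives no basis for it, and does not relate it to 500 nmol. That mismatch follows from the Protocol's own figures and needs no assumption.

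The size of the noise problem depends on a reading that the text leaves open: about 12% to 42% of unchanged patients if the rule is per patient (assumed CVs 5% to 30%), or about 0.01% to 10% for a group mean (assumed CVs 10% to 30%, 40 improvers). Both sets rest on log-normal variation and single samples. Because the outcome is exploratory, carries no power claim and sits beside a planned between-group comparison, severity is modest.

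**What to change.** Restate item 5 as the comparison already planned in the power calculation section: the difference between the good- and poor-adherence groups in 4-month P-cortisol, adjusted for each patient's first value, with a 95% CI. Name the sample (0 or 30 minutes). State who forms the two groups, since that section speaks both of continued poor adherence and of dividing all 80 patients. Drop the 8% threshold as the definition of impairment.

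If a patient-level count is kept, reconcile its definition with the 500 nmol statements in the hypothesis, primary outcome and outcome 1. Say how patients already below that level are handled, and report the count in both adherence groups so that the chance rate is visible.

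The cost is one sentence and a simple regression. Both tests are already scheduled, so no new data are needed. What is given up is a yes/no statement about impairment. The comparison remains observational, because adherence is not randomised.
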